2.5.3 Thiazolidinediones

The thiazolidinediones (TZDs, glitazones) are a class of drugs developed to treat type 2 diabetes because of their insulin sensitizing effect in states of insulin resistance. Studies have shown that the benefits of TZDs are at least partly explained by their ability to improve insulin responsiveness in adipose tissue and reduce inappropriate peripheral lipolysis.^{41,42} As ligands for the nuclear transcription factor peroxisome proliferator-activated receptor gamma (PPAR γ), this class of drugs has multiple complex effects. Improved insulin signaling has been attributed to the ability of TZDs to induce adjocyte differentiation and also prevent the inhibitory effect of c-Jun N-terminal kinases (JNKs) on post-receptor insulin signaling. Pilot studies indicated that the TZDs rosiglitazone and pioglitazone might improve the histology of NASH. Placebo controlled trials have had somewhat mixed results with the French FLIRT trial showing primarily improvement in steatosis^{43,44} and other trials showing improvement in inflammation as well.⁴⁵⁻⁴⁷ The pioglitazone treated patients in the PIVENS trial did not achieve the pre-defined histological endpoint or demonstrate improved fibrosis, but did have significant improvements in steatosis, inflammation, and the presence of steatohepatitis.⁴⁸ Similar to findings in other trials of TZDs, the improvement in ALT occurred over 3-6 months and was not sustained when the drug was discontinued. Whether the histological improvement occurs in parallel with the ALT decrease is unknown since no trial has examined serial liver biopsies in TZD treated patients. The primary side effect of using TZDs over the typical 1-2 year time course of most trials is significant weight gain in some subjects. Exacerbation of congestive heart failure, osteoporosis with distal limb fractures, and rare idiosyncratic hepatotoxicity are additional side effects known to occur with the use of TZDs, but in general they have not been observed in the relatively small NASH trials. This class of medication has not yet been tested and proven safe in children.

2.5.4 Vitamin E

Trials of antioxidant agents for the treatment of NASH have been undertaken because of the proposed role of oxidant stress in the pathogenesis of steatohepatitis.⁴⁹ Vitamin E (RRR-alpha-tocopherol) has been of particular interest. Pilot studies were inconclusive but the PIVENS trial demonstrated that 43% of patients treated for two years reached the desired histological endpoint compared to 19% in the placebo group (P<0.01).⁴⁸ Improvement in fibrosis was not observed. Similar to the pioglitazone-treated patients, the ALT improved over a time period of 3-6 months. Unlike treatment with pioglitazone, weight gain was not observed, but neither was any improvement in insulin sensitivity.

An open-label pilot study of vitamin E in 11 children with suspected NAFLD based on ultrasound showed improvement in serum aminotransferases in all subjects, without concomitant weight loss. Subsequent studies have shown conflicting results. In a 1-year trial of 88 children with biopsy-proven NAFLD, Nobili et al evaluated the effect of 600 IU/day of vitamin E and 500 IU/day of vitamin C or placebo on serum aminotransferases and prevalence of NAFLD by ultrasound.⁵⁰ Both the treatment group and the control group also received nutritional and physical activity counseling, with monthly 1-hour sessions with a dietitian. Serum ALT decreased in both the treatment and placebo group, but was not significantly different between groups.

2.5.5 Cysteamine

The final common pathway by which steatosis develops into steatohepatitis is likely to be mediated through oxidative stress due to reactive oxygen species (ROS) and decreased anti-oxidant

defense.⁵¹ ROS can be generated in the liver through multiple mechanisms including cytochrome P450, nicotinamide adenine dinucleotide phosphate (NADPH) oxidase and lipooxygenase.⁵² Insulin resistance and hyperinsulinism have been shown to increase hepatic oxidative stress and lipid peroxidation through increased hepatic CYPE21 activity. Glutathione (gamma-glutamyl-cysteinylglycine: GSH) is a major endogenous antioxidant and its depletion is implicated in the development of hepatocellular injury. One example of acute glutathione deficiency is acetaminophen poisoning. After a toxic dose of acetaminophen, excess metabolite (N-acetyl-benzoquinoneimine) covalently binds to hepatic proteins and enzymes resulting in liver damage.^{53,54} Restoring glutathione levels can have a protective effect through the reduction of ROS. Glutathione itself does not enter easily into cells, even when given in large amounts. However, glutathione precursors do enter into cells and have been shown to be effective in the treatment of conditions such as acetaminophen toxicity by preventing significant GSH depletion. Examples of GSH precursors include cysteine, Nacetylcysteine, methionine, and other sulphur-containing compounds such as cysteamine. Studies in mice and humans showed oral and intravenous cysteamine to be effective in preventing acetaminophen-induced hepatocellular injury. However, because cysteamine has been associated with gastrointestinal symptoms and because of its previously poor commercial availability, drugs such as N-acetylcysteine have become the mainstay for treatment of acetaminophen poisoning. In fact, Nacetylcysteine has also recently been used in the treatment of NASH. In reports from Turkey, obese individuals with NASH treated with N-acetylcysteine for 4-12 weeks did have an improvement in aminotransferase levels and GGT even though there was no reported change in subject BMI.⁵⁵ This study suggests that increasing GSH levels may be a therapeutic strategy for the treatment of NAFLD.

Recent studies have suggested that the conditionally essential amino acid cysteine is a major limiting factor for GSH synthesis, and the factors (e.g., insulin and growth factors) that stimulate cysteine uptake by cells generally result in increased intracellular GSH levels.^{56,57} Cysteamine, a GSH precursor, is a small molecule (HS-CH₂-CH₂-NH₂) which is able to cross cell membranes easily. Cysteamine is believed to react with extracellular cystine to form cysteine which then is readily taken up into the cell and transformed into GSH. When ingested, much of the cysteamine is thought to be taken up by the liver, and may therefore deliver optimal "anti-oxidant effect" to this organ. Cysteamine is currently available and is used in the treatment of cystinosis, an intra-lysosomal cystine storage disorder.⁵⁸

[figure not shown]
In cystinosis, cysteamine acts by converting cystine to cysteine and cysteine-cysteamine mixed disulfide which are then both able to leave the lysosome through the cysteine and lysine transporters respectively.⁵⁸ Within the cytosol, the mixed disulfide can be reduced by its reaction with glutathione and the cysteine released can be used for further GSH synthesis. The synthesis of GSH from cysteine is catalyzed by two enzymes, gamma-glutamylcysteine synthetase and GSH synthetase. This pathway occurs in almost all cell types, with the liver being the major producer and exporter for GSH. The reduced cysteine-cysteamine mixed disulfide will also release cysteamine, which, in theory is then able to re-enter the lysosome, bind more cystine and repeat the process.⁵⁹ In a recent study in children with cystinosis, enteral administration of cysteamine resulted in increased plasma cysteamine levels. which subsequently caused prolonged efficacy in the lowering of leukocyte cystine levels.⁵⁹ This may have been due to "re-cycling" of cysteamine when adequate amounts of drug reached the lysosome. If cysteamine does act in this fashion, then GSH production may also be significantly enhanced. Hepatic fat accumulation and oxidative stress contribute to the pathogenesis of NAFLD. Recently, an open-label pilot trial of the thiol agent cysteamine bitartrate (Cystagon[®]) for biopsy-proven pediatric NAFLD and elevated ALT was completed to evaluate the safety and potential efficacy of entericcoated cysteamine therapy for NAFLD in children.⁶⁰ Cysteamine bitartrate readily crosses cellular membranes and is FDA approved for the treatment of the lysosomal storage disorder cystinosis. Eleven of thirteen children were enrolled and completed EC-Cysteamine therapy. For these 11

children with NAFLD, mean ALT decreased significantly from a mean of 120 U/L at baseline to 55 U/L after 6 months of treatment. There was a similar significant reduction in AST.

3. Study design

3.1 Design overview

CyNCh is a multicenter, double-masked, randomized, placebo-controlled, phase IIb clinical trial of treatment with either cysteamine bitartrate DR capsules (300 mg orally twice daily for patients < 65 kg, 375 mg orally twice daily for patients >65-80 kg or 450 mg orally twice daily for patients >80 kgkg) or placebo for children with histologically-confirmed NAFLD. Eligible patients will be randomized to receive either cysteamine bitartrate DR or placebo capsules orally twice a day for 52 weeks. Patients ≤ 65 kg will have a starting dose of 150 mg per day (one 75 mg capsule twice daily) with dose escalation to 600 mg per day (four 75 mg capsules twice daily); patients weighing >65-80 kg at randomization will start with a dose of 300 mg per day (two 75 mg capsules twice daily) with a dose escalation to 750 mg per day (five 75 mg capsules twice daily) and patients >80 kg will start with a dose of 450 mg per day (three 75 mg capsules twice daily) with dose escalation to 900 mg per day (six 75 mg capsules twice daily). The patients will return for a follow-up visit at week 4 to ensure that they have reached the full dose as planned and that any side effects are identified and managed. The patients will return for follow-up visits approximately every 12 weeks after randomization (weeks 12, 24, 36, and 52). There will be a 24 week post-treatment follow-up period at the end of the treatment phase to assess the durability of effects, if any, and to ensure patient safety following the end of treatment (week 76). The study design can be schematically shown as below:

• Randomized, multi-center, double-masked, placebo-controlled trial

· Cysteamine bitartrate delayed-release, twice daily, compared to placebo

3.2 Treatment groups

Participants who have signed an informed assent statement along with their parent signing an informed consent statement and who meet the eligibility criteria will be randomly assigned to one of

two groups for 52 weeks of treatment. The dose of cysteamine bitartrate DR assigned will be either 600 mg/day (four 75 mg capsules twice daily) for patients \leq 65 kg; 750 mg/day (five 75 mg capsules twice daily) for patients >65 - 80 kg, or 900 mg/day (six 75 mg capsules twice daily) for patients >80 kg. Patients in the placebo group will be assigned corresponding numbers of capsules based on their baseline body weight. Patients \leq 65 kg at baseline will take four 75 mg capsules twice daily; patients >65 kg - 80 kg will take five 75 mg capsules twice daily and those patients greater than 80 kg at baseline will take six 75 mg capsules twice daily. The number of capsules taken will be increased gradually during weeks 1-4 to the assigned number and remain fixed thereafter regardless of weight changes after randomization according to the following schemes:

• Group 1: cysteamine bitartrate DR:

- 600 mg/day (four 75 mg capsules twice daily) for patients $\leq 65 \text{ kg}$ at baseline
- 750 mg/day (five 75 mg capsules twice daily) for patients >65 80 kg at baseline
- 900 mg/day (six 75 mg capsules twice daily) for patients >80 kg at baseline
- Group 2: cysteamine bitartrate DR placebo (as identical capsules to active drug)
 - 600 mg/day (four 75 mg capsules twice daily) for patients \leq 65 kg at baseline
 - 750 mg/day (five 75 mg capsules twice daily) for patients >65 80 kg at baseline
 - 900 mg/day (six 75 mg capsules twice daily) for patients >80 kg at baseline

The randomization scheme will assign patients into two groups to receive either cysteamine bitartrate DR or placebo. The randomization design will be stratified by clinical center and baseline body weight into one of three categories (less than or equal to 65 kg, greater than 65 kg up to 80 kg, or greater than 80 kg; with assignments in permuted blocks of random length within each stratum to achieve a target dose of 9 to 12 mg/kg per day up to a maximum total dose of 600-900 mg per day (children with weights exceeding 100 kg will receive a dose of 900 mg per day). This scheme will ensure that the two groups will be balanced by calendar time of enrollment (to minimize secular effects) and by clinic (to minimize clinic-specific effects of differences in patient populations and management).

The randomization plan will be prepared and administered centrally by the Data Coordinating Center (DCC) but will not require real time interaction with a DCC staff member. Requests for randomizations will be made by the clinics using a web-based application. An assignment will be issued only if the database shows that the patient is eligible, has signed the consent/assent statement, and has had all required baseline data keyed into the database.

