3.3 Study drug dosing schedule

Study drugs will be shipped to each clinical center's pharmacy. The research pharmacy staff will then provide the study staff with masked study drug bottles based on the DCC randomization schedule. Patients will be dispensed bottles labeled "Cysteamine bitartrate delayed-release 75 mg capsules or placebo". Study drug should be taken 30 minutes prior to a meal.

Patients will be on a dose escalation regimen, the number of capsules taken will be increased gradually during weeks 1-4 to the assigned number and remain fixed thereafter regardless of weight changes according to the following schemes:

For patients with a baseline weight of 65 kg or less:

- Week 1: One 75 mg capsules orally twice a day (1 in the morning and 1 in the evening) (150 mg/day),
- Week 2: Two 75 mg capsules orally twice a day (2 in the morning and 2 in the evening (300 mg /day)
- Week 3: Three 75 mg capsules orally twice a day (3 in the morning and 3 in the evening) (450 mg/day)
- Weeks 4-52: Four 75 mg capsules orally twice a day (4 in the morning and 4 in the evening) (600 mg/day)

For patients with a baseline weight greater than 65 kg up to 80 kg:

- Week 1: Two 75 mg capsules orally twice a day (2 in the morning and 2 in the evening) (300 mg /day)
- Week 2: Three 75 mg capsules orally twice a day (3 in the morning and 3 in the evening) (450 mg/day)
- Week 3: Four 75 mg capsules orally twice a day (4 in the morning and 4 in the evening) (600 mg/day)
- Weeks 4-52: Five 75 mg capsules orally twice a day (5 in the morning and 5 in the evening) (750 mg/day)

For patients with a baseline weight greater than 80 kg:

- Week 1: Three 75 mg capsules orally twice a day (3 in the morning and 3 in the evening) (450 mg/day)
- Week 2: Four 75 mg capsules orally twice a day (4 in the morning and 4 in the evening) (600 mg/day)
- Week 3: Five 75 mg capsules orally twice a day (5 in the morning and 5 in the evening) (750 mg/day)
- Weeks 4-52: Six 75 mg capsules orally twice a day (6 in the morning and 6 in the evening) (900 mg/day)

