3.3.1 Cysteamine DR

Cysteamine DR will be taken orally twice daily 30 minutes prior to meals (morning/breakfast and evening/dinner) for weeks 1-52. The rationale for the 9 mg/kg to 12 mg/kg daily dose range of cysteamine DR is that this target dose was the best tolerated in the pilot study and had the greatest benefit ⁶⁰.

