4.2 Inclusion criteria

Patients must satisfy all of the following criteria to be eligible for enrollment:

- Children age 8-17 years inclusive.
- Liver biopsy within 90 days of screening visit and not more than 120 days before randomization.
- Clinical history consistent with NAFLD.
- Definite NAFLD based upon liver histology.
- No evidence of any other liver disease by clinical history or histological evaluation
- A histological severity of NAFLD Activity Score (NAS) \geq 4.
- Sexually active female participants of childbearing potential (i.e., not surgically sterile [defined as tubal ligation, hysterectomy, or bilateral oophorectomy) must agree to utilize the same two acceptable forms of contraception from screening through completion of the study and to complete a pregnancy test at each study visit. The acceptable forms of contraception for this study include hormonal contraceptives (oral, implant, transdermal patch, or injection) at a stable dose for at least 1 month prior to screening, and barrier (condom with spermicide, diaphragm with spermicide). Sexual activity will be ascertained at each study visit for post-menarchal females and if sexually active, subject must verify use of the same 2 acceptable forms of contraception.
- Participants must be able to swallow cysteamine bitartrate DR capsules.
- Written informed consent from parent or legal guardian.
- Written informed assent from the child.

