6.11 Procedures for unmasking treatment assignment

Treatment assignments are double masked throughout the study until all data collection for the CyNCh trial has been completed (i.e., after completion of the 24 week post trial follow-up for all participants). Every effort will be made to maintain the masking throughout the study except in emergencies. The code of specific pharmacological treatment will not be broken without the knowledge of the clinical center's principal investigator and the study leadership.

Unmasking of study medication may occur under the following conditions:

- Severe allergic reaction (Stevens-Johnson Syndrome): Study medication is stopped indefinitely. The patient, primary care provider (PCP), and the investigator may be unmasked.
- **Pregnancy during the study:** Study medication will be stopped indefinitely, and the coded medication may be unmasked. The patient, PCP, and investigator will be notified of the associated risks of teratogenicity.
- **Development of hepatotoxicity:** Hepatotoxicity will be defined as the development of jaundice with a serum direct bilirubin of > 1.0 mg/dL and an increase in the baseline ALT and AST value that is two-fold or > 400 U/L during treatment. Study medication will be discontinued; however, there will be no unmasking until study conclusion.

The Data and Safety Monitoring Board will review all instances of unmasking that occur.

7. Statistical design and analysis

7.1 Primary hypothesis:

Cysteamine bitartrate DR at 9-12 mg/kg orally daily for 52 weeks is better than placebo in improving liver histologic parameters as measured by the NAFLD activity score in children with NAFLD.

Secondary aims:

- To assess safety and tolerability of cysteamine DR during the 52 week treatment period
- To assess the effect of cysteamine DR on:
 - Serum alanine aminotransferase (ALT), serum aspartate aminotransferase (AST) and serum γ -glutamyl transferase (GGT).
 - Liver fat as measured by MRI.
 - Markers of oxidation and anti-oxidant status: malondialdehyde, F2 alpha-isoprostane, total antioxidant capacity
 - o Insulin resistance
 - Anthropometrics
 - o Quality of Life
 - o Liver related symptoms

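### The weight bands give 9-12 mg/kg/day only for baseline weights of 50 to 100 kg; children under 50 kg are assigned more, and no section says so

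*Protocol*

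**What the plan says.** The Synopsis and Protocol 3.2 describe randomization stratified by clinical center and three baseline weight bands, "to achieve a target dose of 9 to 12 mg/kg per day up to a maximum total dose of 600-900 mg per day". Section 3.2 adds that "children with weights exceeding 100 kg will receive a dose of 900 mg per day".

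Section 3.3.1 justifies the range from the pilot study: "The rationale for the 9 mg/kg to 12 mg/kg daily dose range of cysteamine DR is that this target dose was the best tolerated" and, it says, gave the greatest benefit. Section 7.1 puts the same range into the primary hypothesis: "Cysteamine bitartrate DR at 9-12 mg/kg orally daily for 52 weeks is better than placebo".

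The doses themselves are in 3.2 and 3.3. The lowest band is defined as "For patients with a baseline weight of 65 kg or less" and receives 600 mg/day from week 4. The band above 65 and up to 80 kg receives 750 mg/day, and the band above 80 kg receives 900 mg/day. The number of capsules is then held constant whatever happens to weight.

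On entry, 4.2 requires "Children age 8-17 years inclusive". Neither 4.2 nor 4.3 contains a body-weight criterion for the trial.

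Section 6.2 gives a second rationale for the lowest band. It reports a clinical response in the pilot at 300 mg twice daily, says that this dose was chosen for children of 65 kg or less, and describes gastrointestinal tolerance as satisfactory (nausea or abdominal pain in 2 of 13 children, resolving in under two weeks).

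**The concern.** A per-kilogram range can be met by a fixed dose only between two body weights. The lowest band has an upper limit but no lower one, and recruitment starts at age 8 with no weight floor. At some weight within that band the assigned dose must therefore exceed 12 mg/kg/day. The highest band is open at the top, so the dose must drop below 9 mg/kg/day at some weight there.

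The protocol acknowledges the upper end in 3.2 but nowhere mentions the lower end. A cap expressed as a maximum daily dose explains why heavy children receive less per kilogram. It cannot explain why light children receive more.

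Two things are at stake. The first is wording: the primary hypothesis names an exposure that the schedule does not give to every eligible child. The second is the reach of the rationale: 3.3.1 supports 9-12 mg/kg/day on tolerability and benefit, and a child assigned 15 mg/kg/day lies outside what that section claims to support.

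**Working it through.** **Inputs.** Daily doses of 600, 750 and 900 mg for baseline weights of 65 kg or less, above 65 to 80 kg, and above 80 kg (3.2, 3.3). Target of 9 to 12 mg/kg/day (Synopsis, 3.2, 3.3.1, 7.1).

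**Step 1: weights at which each dose meets the target.** The lower weight is dose/12 and the upper weight is dose/9.

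| Dose (mg/day) | dose/12 (kg) | dose/9 (kg) | Band as defined | Part of the band that complies |
|---|---|---|---|---|
| 600 | 50.0 | 66.7 | 65 kg or less | 50 to 65 kg |
| 750 | 62.5 | 83.3 | above 65 to 80 kg | all |
| 900 | 75.0 | 100.0 | above 80 kg | above 80 to 100 kg |

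The stated range is thus reproduced for 50 to 100 kg without a gap. At the band limits:

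- 600/50 = 12.0 and 600/65 = 9.2
- 750/65 = 11.5 and 750/80 = 9.4
- 900/80 = 11.25 and 900/100 = 9.0

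**Step 2: below 50 kg.** The example weights are assumptions.

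- 49 kg: 600/49 = 12.2
- 45 kg: 600/45 = 13.3
- 40 kg: 600/40 = 15.0
- 35 kg: 600/35 = 17.1
- 30 kg: 600/30 = 20.0

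**Step 3: above 100 kg.** Again with assumed weights.

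- 110 kg: 900/110 = 8.2
- 120 kg: 900/120 = 7.5

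**Step 4: the two rationales side by side.** Section 3.3.1 supports a mg/kg range; 6.2 supports a flat 600 mg/day. By step 1 they describe the same exposure only for children of 50 to 66.7 kg. The protocol does not give the pilot children's weights, so it does not show that the two rationales agree below 50 kg.

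**Not used.** Weeks 1 to 3 are a planned escalation, and later weight change shifts mg/kg because the capsule count is fixed. The point relies on neither; all figures are the assigned full dose over baseline weight.

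**The case against.** Several points on the other side are sound.

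- **The bands mostly work.** A reader might infer that they fail to deliver the target in general. They do not: all three comply between 50 and 100 kg, and three bands of 75 mg capsules can only approximate a per-kilogram target.
- **The upper shortfall is declared.** A reader might count weights above 100 kg as an equal, hidden error. Section 3.2 states the 900 mg/day cap in the sentence that gives the target. All that remains is that 7.1 does not repeat it.
- **The lowest band has its own support.** A reader might infer that nothing in the protocol supports tolerability in the lightest children. Section 6.2 argues for 300 mg twice daily as a flat dose. It also sets the trial's average of 0.470 g/m²/day against 1.30-1.95 g/m²/day in cystinosis. For an assumed child of 30 kg and 130 cm (Mosteller surface area about 1.04 m²), 600 mg/day is 0.6/1.04, or about 0.58 g/m²/day, still under half of 1.30. This stands, but without pilot weights it does not show that light children were represented.
- **The inference is intact.** A reader might infer that the trial cannot answer its primary question. The primary analysis compares assigned groups by intention to treat, the Synopsis defines treatment by the capsule doses, and the primary objective names no mg/kg figure. Weight band is also a randomization stratum.
- **Numbers affected.** A reader might take it as certain that some participants fall outside the range. The entry criteria allow it, but no weight distribution is given.

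The argument that 9-12 mg/kg is merely a target carries less weight. Section 7.1 states it as the exposure under test, and 3.3.1 builds the dose rationale on it.

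**Conclusion.** The protocol contradicts itself at the low end. Any child under 50 kg at baseline is assigned more than 12 mg/kg/day, against the target in the Synopsis, 3.2 and 3.3.1 and the exposure in 7.1, and no section acknowledges it. The 50 kg threshold is exact. The size of the excess depends on weight: 11% over the limit at 45 kg (13.3/12) and 25% at 40 kg (15.0/12), both weights being assumptions. The share of children affected cannot be derived from the protocol.

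At the high end the only defect is that 7.1 omits an exception that 3.2 states.

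The effect is on description and scope: which exposure a conclusion may name, and which children the mg/kg rationale covers. The randomized comparison, type I error and power do not change. The correction is worth making because it is cheap and because the hypothesis states a property that the schedule does not have. The protocol does not show that any dose in the schedule is wrong, and this point does not say so.

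**What to change.** 1. Reconcile the Synopsis, 3.2, 3.3, 3.3.1, 6.2 and 7.1 so that the stated exposure is the one that the schedule gives, at both open ends of the weight range. Which text changes is a clinical decision for the sponsor.
2. State how the flat-dose rationale in 6.2 relates to the mg/kg rationale in 3.3.1 for children under 50 kg, giving the pilot weights if they are available.
3. Report the distribution of baseline mg/kg in the active arm; in the placebo arm the figure is nominal only.
4. Give the DSMB adverse events by arm and mg/kg class (below 9, 9-12, above 12). Section 6.10.2 already lets the DSMB request subgroup summaries, and weight is already measured at screening and follow-up.

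The cost is protocol wording and one table. The outer classes may be small, so the table is descriptive and should not be read as a test. Sample size, randomization and the primary analysis stay as they are.
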